#### 7.1.2. Renal Dysfunction

For subjects who may experience impaired renal function during the course of the study, whose CrCl declines to  $<30 \text{ mL/min}/1.73\text{m}^2$ , dalteparin sodium may need to be adjusted and Anti-Xa levels should be monitored to maintain appropriate levels (ie, trough Anti-Xa levels of  $<0.4 \text{ IU/mL}$ ) and the medical monitor should be notified. Subjects with major bleeding or bleeding disorders such as Platelet Dysfunction, Protein Deficiency, Disseminated Intravascular coagulation (DIC), Factor Deficiency, Hemophilia, Idiopathic Thrombocytopenic Purpura (ITP) or Von Willebrand Disease at the time of the Screening Visit or an unacceptably high risk of bleeding, at the discretion of the investigator, should not be considered candidates.

- To assess for bioaccumulation of dalteparin sodium, trough Anti-Xa levels should be checked prior to the next dose. The trough Anti-Xa levels should be <0.4 IU/mL;
- If the Anti-Xa level is above 0.4 IU/mL, the dose of dalteparin sodium should be reduced by either holding one dose or reducing by 25 IU/kg, or by doing both;
- The Anti-Xa measurement should be repeated after the next dose. The actual dosing time prior to the repeat plasma sample draw and the actual time of the repeat sample draw must be recorded.

## **7.2. Use of Other Anticoagulants**

No other systemic anticoagulants are allowed during the study with the exception of allowance of hospital specific IV line patency protocols which could include tPA and 3 IU/kg dose of unfractionated heparin or transient use of another LMWH or un-fractionated heparin for no longer than 48 hours, if the subject is unable to be treated with study drug due to an unanticipated hospital admission or a clinical event.

Subjects are excluded if they received unfractionated heparin within 3 hours, or LMWH within 12 hours, of the first dose of dalteparin.

## **7.3. Identity of Investigational Product(s)**

The medication used in this study will be dalteparin sodium (Fragmin®), supplied in open-label format as the following:

- Multiple dose vials of 25,000 IU/1 mL (3.8mL for US or 4mL for ROW) containing preservative benzyl alcohol;
- Preservative-free single dose vials of 2,500 IU/1 mL (4mL) [where available];
- Preservative-free 10,000 IU / 1 mL single-dose graduated syringe (can be diluted as needed per the IP Manual).

The multidose vials utilized in this study include a preservative. The single-dose pre-filled syringe and single-dose vial are preservative-free.

Only study subjects that are hospital in-patients can receive the 10,000 IU/1mL dosage form, diluted to 2,500 IU/mL. If a study subject is an out-patient and will be administered study drug at home by a caregiver, they must use either the 2,500 IU / 1 mL preservative-free 4 mL vial to prepare the prescribed dose or the 10,000 IU / 1 mL preservative-free syringe undiluted to prepare the prescribed dose. The 10,000 IU / 1 mL preservative-free syringe must not be further diluted when prepared at the study subject's home.

Each of the above three study medication presentations can be dispensed to subjects when they are out-patients, however, not if they require dilution.

## 7.4. Labeling and Packaging of Treatments

The study medication, dalteparin sodium (Fragmin®), will be manufactured by Pfizer Inc. and packaged and distributed by a designated vendor in accordance with instructions provided by Pfizer Inc. Pfizer Inc will also provide the 0.5 mL and 1.0 mL Tuberculin (TB) latex-free, micro-dosing syringes as well as sterile empty vials for evacuation.

Each carton will contain a clinical label including text to meet the country regulatory requirements and include but not limited to the following information: sponsor name, protocol number, storage conditions, contents and directions for use.

Cartons with multidose and single-dose vials will contain 1 vial per carton. Cartons with pre-filled syringes will contain 36 syringes per carton.

Refer to the tables in [Appendix 2](#) for guidance on subjects dosing requirements.

Dosing of the 10,000 IU/1 mL pre-filled syringe formulation should not be administered directly via the original pre-filled syringe unless the intended patient dose is exactly 10,000 IU/1 mL. All other doses using the 10,000 IU/1 mL pre-filled syringe presentation should be evacuated into a sterile vial and administered via a separate syringe to ensure accurate patient dosing. For full preparation and administration information on all three investigational product presentations refer to the Investigational Product Manual.

### 7.4.1. Storage

The investigator or an approved representative, eg, pharmacist, will ensure that all investigational products (including any comparator and/or marketed products) are stored in a secured area with controlled access under required storage conditions and in accordance with applicable regulatory requirements.

Investigational products should be stored in their original containers and in accordance with the labels.

See the Investigational Product (IP) manual or package insert for storage conditions of the product once diluted.

Any storage conditions stated in the single reference safety document (SRSD) will be superseded by the storage conditions stated on the product label.

Site systems must be capable of measuring and documenting (for example, via a log), at a minimum, daily minimum and maximum temperatures for all site storage locations (as applicable, including frozen, refrigerated, and/or room-temperature products). This should be captured from the time of investigational product receipt throughout the study. Even for continuous-monitoring systems, a log or site procedure that ensures active evaluation for excursions should be available. The intent is to ensure that the minimum and maximum temperature is checked each business day to confirm that no excursion occurred since the last evaluation and to provide the site with the capability to store or view the minimum/maximum temperature for all non-working days upon return to normal operations. The operation of the temperature monitoring device and storage unit (for example, refrigerator), as applicable, should be regularly inspected to ensure they are maintained in working order.

Any excursions from the product label storage conditions should be reported to Pfizer upon discovery. The site should actively pursue options for returning the product to the storage conditions described in the labeling, as soon as possible. Deviations from the storage requirements, including any actions taken, must be documented and reported to Pfizer.

Once an excursion is identified, the investigational product must be quarantined and not used until Pfizer provides permission to use the investigational product. It will not be considered a protocol deviation if Pfizer approves the use of the investigational product after the temperature excursion. Use of the investigational product prior to Pfizer approval will be considered a protocol deviation. Specific details regarding information the site should report for each excursion will be provided to the site.

Receipt of materials, door opening and closing, and other routine handling operations where the products are briefly out of the temperature range described in the labeling are not considered excursions.

#### **7.4.2. Drug Supplies**

For full Investigational product details, please refer to the Investigational Product Manual.

Drug supply will be provided to sites after the site's Investigator Initiation Package (IIP) documents are received and approved. All drug supplies for this study must be stored according to labeled storage conditions. If any excursion from the recommended storage (per study drug label) occurs, the study monitor or other sponsor study team member must be consulted before using the study drug.

Two different size syringes (1 mL TB syringe and 0.5 mL TB syringe) will be available to all sites. Investigators will use their clinical judgment regarding which size syringe is most applicable for administration of each subject's individual study drug dose level.

#### **7.4.3. IP Accountability Log**

The Investigator or delegated personnel on the study site must maintain records of the receipt of study drug to the study site, the inventory at the site, the amount dispensed to each subject, and the return of the unused study medication by the subject to the Investigator.

The sponsor or designee will provide guidance on the destruction of unused investigational product (eg, at the site). If destruction is authorized to take place at the study site, the investigator must ensure that the materials are destroyed in compliance with applicable environmental regulations, institutional policy, and any special instructions provided by Pfizer and all destruction must be adequately documented.

All used syringes will be disposed as per local biohazard requirements.

The IP Accountability Log must be available for monitoring, auditing or inspection. Details of the accountability of clinical supplies will be recorded.

## 8. ADMINISTRATION OF TREATMENTS

All subjects will be dosed based on age, weight, and anti-Xa levels. After the Baseline evaluations have been completed, subjects will receive their first dose of study medication by subcutaneous injection according to the following dosing administration instructions below:

- Patients should be sitting or lying down for FRAGMIN® deep subcutaneous administration injection. Based on experience in adults, dalteparin sodium (Fragmin®) should be injected in a U-shape area around the navel, the upper outer side of the thigh or the upper outer quadrangle of the buttock. However, other sites may be more suitable for pediatric patients. Using the thumb and forefinger, you must lift up a fold of skin while giving the injection. The entire length of the needle should be inserted at a 45 to 90 degree angle. The injection site should be varied daily;
- If a subject receives a partial dose due to a dosing error, a second dose should not be given to supplement the initial partial dose. This should be stressed to parents and caregivers if administering study drug to subjects who are out-patients and to hospital staff that will dose the study subjects who are in-patients;
- Clinical supply that is unused by one subject and returned to the site cannot be redispensed for another visit for the same subject or be redispensed to a different subject.

### 8.1. Dosing Groups:

1. Subjects ages 0 (greater than or equal to 36 weeks gestation) to less than 8 weeks will receive an initial dose of 125 IU/kg twice daily by subcutaneous injection of **preservative-free solution ONLY** supplied in single-dose prefilled graduated syringes, containing 10,000 IU/1 mL or preservative-free 4 mL single-dose vials containing 2,500 IU/1 mL if available. If the 2,500 IU/1 mL vials are not available, the 10,000 IU/1 mL dosage form can be diluted in the hospital pharmacy to 2,500 IU/1 mL by a trained pharmacist or pharmacy technician as needed, according to the suggested dilution process outlined in the IP Manual.
2. Subjects aged greater than equal to 8 weeks to less than 2 years will receive an initial dose of 150 IU/kg twice daily by subcutaneous injection of **preservative-free solution ONLY** supplied in single-dose prefilled graduated syringes, containing 10,000 IU/1 mL, or preservative-free 4 mL single-dose vials containing 2,500 IU/1 mL if available. If the 2,500 IU/mL vials are not available, the 10,000 IU/1 mL dosage form can be diluted in the hospital pharmacy to 2,500 IU/1 mL by a trained pharmacist or pharmacy technician as needed, according to the suggested dilution process outlined in the IP Manual.
3. Subjects aged greater than or equal to 2 years to less than 8 years and subjects ages greater than or equal to 8 years to less than 12 years will receive an initial dose of 125 IU/kg by subcutaneous injection of preservative-free solution supplied in prefilled syringes containing 10,000 IU/1 mL, or preservative-containing 95,000 IU/3.8 mL (US) or 100,000/4mL (Europe) (25,000 IU/1 mL) multidose vials. For smaller doses, preservative-free 4 mL single dose vials containing 2,500 IU/1 mL

may be used for dose preparation if available. If the 2,500 IU/1 mL vials are not available, the 10,000 IU/1 mL dosage form can be diluted in the hospital pharmacy to 2,500 IU/1 mL by a trained pharmacist or pharmacy technician as needed, according to the suggested dilution process outlined in the IP Manual.

4. Subjects aged greater than or equal to 12 years to less than 19 years will receive an initial dose of 100 IU/kg by subcutaneous injection of preservative-containing solution supplied in either preservative-free pre-filled syringes prefilled syringes containing 10,000 IU/1 mL or preservative containing 95,000 IU/3.8 mL (25,000 IU/1 mL) multidose vials.
  - If hospitalized during the Dose Adjustment and PD Phases, all doses will be prepared daily by the trained hospital staff. After hospital discharge, study drug will be dispensed to the parents/guardians who will be trained in the handling and storage of the study drug. If a subject receives a partial dose due to a dosing error, a second dose should not be given to supplement the initial partial dose. This should be stressed to parents and caregivers if administering study drug to subjects who are out-patients and to hospital staff that will dose the study subjects who are in-patients.

While subjects are in-patients at the hospital, study drug administration will be conducted by the delegated, trained investigative site staff, or, delegated other hospital personnel who are trained by the Investigator regarding correct study drug administration. When subjects are released from the hospital, the designated parents/guardians will be trained by the Investigator regarding correct study drug dosing and administration. The trained parents/guardians will dose and administer study drug to the subjects at home.

If parents/guardians are not deemed capable or are not willing to administer study drug to the subjects when they are released from the hospital, a visiting nurse, may be trained and made available by the Principle Investigator (PI) or designee, to prepare and administer a daily dose for subjects as needed, if this service is available through the investigative site..

To calculate dosing volumes refer to the protocol dosing directions below. Subjects weighing greater than 3 kg and less than or equal to 100.1 kg are allowed in the study. For age- and weight-based dosing calculations, see [Appendix 2](#).

- For subjects 0 ( $\geq 36$  weeks gestation) to  $< 2$  year of age, weighing  $\geq 3.0$  kg: Preservative-free dosing solutions must be used in these subjects. The final dose is to be prepared by drawing up the appropriate dose of drug solution into the appropriate syringe supplied;
- For subjects  $\geq 2$  years to  $< 12$  years: Withdraw dosing volume needed (obtained from dosing charts) from the 95,000 IU/3.8 mL (25,000 IU/1 mL) multidose vial using a 1.0 mL micro-dosing syringe or per Investigator's judgment, the 2,500 IU/1mL single dose vial **or**, utilize the prefilled syringes containing 10,000 IU/1 mL labeled Fragmin® (dalteparin sodium), for the required dose. Note that if the required dose is exactly 10,000 IU/mL, the dose can be administered directly from the pre-filled syringe.
- For subjects  $\geq 12$  years to  $< 19$  years of age: Withdraw dosing volume needed (obtained from dosing charts) from 95,000 IU/3.8 mL (25,000 IU/1 mL) multidose vial labeled Fragmin® (dalteparin sodium) using a 1.0 mL micro-dosing syringe, or

per the Investigator's judgment or utilize the prefilled syringes containing 10,000 IU/1 mL labeled Fragmin® (dalteparin sodium). Note that if the required dose is exactly 10,000 IU/mL, the dose can be administered directly from the pre-filled syringe.

## 8.2. Dosing Scheme: Three Phases

### 1. Dose Adjustment Phase:

All subjects will receive daily dosing every 12 hours  $\pm$ 1 hour with dalteparin sodium with the final dose from the Dose Adjustment Phase (no less than 8 hours between doses). However, if a dose is not able to be delivered every 12 hours  $\pm$ 1 hour, administer the dose (no less than 8 hours between doses) and record the actual dosing time. The first Anti-Xa plasma sample drawn after the initial dose of study drug treatment should be conducted 4 hours  $\pm$ 1 hour after the first, second or third dose of study medication per Investigator judgment. Subsequent Anti-Xa plasma samples conducted following dose adjustments will also be drawn at 4 hours  $\pm$ 1 hour post-dose, after the first, second or third dose of study medication per Investigator judgment. . If the Anti-Xa level is not within the target therapeutic range of 0.5-1.0 IU/mL, the dose must be adjusted in increments or decrements of 25 IU/kg in order to achieve target Anti-Xa levels (0.5 to 1.0 IU/mL). After dose adjustment, Anti-Xa levels should be measured also after the first, second or third dose per Investigator judgment. If the therapeutic range is not achieved after a maximum of 6 adjustments (up to Day 7), the subject will be withdrawn from the study.

### 2. Pharmacodynamic Phase:

Subjects completing the Dose Adjustment Phase will enter into the PD Phase and will continue with daily dosing every 12 hours  $\pm$ 1 hour with dalteparin sodium with the final dose from the Dose Adjustment Phase (no less than 8 hours between doses). However, if a dose is not able to be delivered every 12 hours  $\pm$ 1 hour, administer the dose (no less than 8 hours between doses) and record the actual dosing time. Subjects will be randomized to two different plasma sampling windows (1 to 3 h and 5 to 8 h or 3 to 5 h and 8 to 12 h) for anti-Xa plasma samples (for the central lab, only) via the Pfizer Interactive Web Response System (IWRS) system, IMPALA (see below). IMPALA will only provide the subject Screening ID number and randomized plasma sampling group assignment (and respective Randomization Number) during the study (it will not manage drug supply inventory). The plasma sampling times can take place over the duration of the PD Phase to avoid blood volume shifts if necessary. If a plasma sample is not drawn during the correct assigned time point, it should be repeated if possible, at the correct time point when appropriate.

The assignment of the plasma sampling time points to the subjects within each age group will be centrally randomized via the IMPALA system (note that only plasma sampling groups will be randomized, not study medication. This is an open-label treatment study).

The two plasma samples will be collected from each subject during the PD Phase based on the subject's assigned plasma sampling randomization group:

- Randomization Schedule A:

- One sample at 1 to 3 hours post-dose;
- One sample at 5 to 8 hours post-dose.
- Randomization Schedule B:
  - One sample at 3 to 5 hours post-dose;
  - One sample at 8 to 12 hours post-dose.

3. **Follow-up Phase:**

In the Follow-Up Phase, subjects will continue daily dosing every 12 hours  $\pm$ 1 hour with dalteparin sodium with the final dose from the Dose Adjustment Phase (no less than 8 hours between doses) until EOS or ET. However, if a dose is not able to be delivered every 12 hours  $\pm$ 1 hour, administer the dose (no less than 8 hours between doses) and record the actual dosing time. In-clinic visits will occur on Visits 5, 6 and 7 for safety, and efficacy assessments, and Anti-Xa plasma samples. Dose adjustments can be made during these visits if necessary. The Principal Investigator or designee will follow-up weekly during a telephone interview with subjects and/or caregivers after discharge from the hospital to assess study compliance and general well-being. Subjects will have repeat imaging (using the same imaging method used at Screening) at the EOS visit or Early Termination (ET) visit to measure clot resolution.

For non-cancer patients who stop dalteparin treatment prior to 3 months according to the ACCP Guidelines, Anti-Xa and Anti-IIa plasma sampling will not be required after study medication discontinuation.

Treatment will continue until any of the following occurs:

- New or progressive VTE (whether symptomatic or asymptomatic);
- Bleeding necessitating permanent discontinuation of anticoagulant therapy;
- Unexpected thrombocytopenia;
- Other AEs necessitating discontinuation of study drug, withdrawal of consent, or scheduled study termination completion;
- Unexpected permanent discontinuation of anticoagulation therapy.

For procedures that require interruption of study treatment, it is recommended to follow the ACCP guidelines. The guidelines state that it may be advisable to omit two doses of LMWH before procedures being performed and resume 12 to 24 hours after the procedures.

### 8.3. Method of Assigning Subjects to Treatment Groups

This is an open label study. All 50 subjects will receive dalteparin sodium (Fragmin®). During the PD Phase, subjects will be centrally randomized to one of two different plasma sampling windows (1 to 3 h and 5 to 8 h or 3 to 5 h and 8 to 12 h) via the Pfizer IWRS system, IMPALA.

### 8.4. Selection of Doses in Study

Dosing in the study was based upon published literature describing the dosing previously used in this subject population with (Fragmin®). Nohe et al have shown that the Anti-Xa levels in these subjects have fallen within the target range of Anti-Xa levels (0.5 to 1.0 IU/mL) using similar dosing.

### 8.5. Blinding

This is an open-label trial.

### 8.6. Prior and Concomitant Therapy

No other systemic anticoagulants are allowed during the study with the exception of allowance of hospital specific IV line patency protocols which could include tPA and 3 IU/kg stat dose of unfractionated heparin, if the subject is unable to be treated with study drug due to an unanticipated hospital admission or a clinical event. Subjects are excluded from the study if they received unfractionated heparin within 3 hours, or LMWH within 12 hours, of the first dose of dalteparin. Use of oral, inserted, injected, implanted or transdermal hormonal methods of contraception is not allowed due to risks of VTE.

## 9. ASSESSMENTS AND ENDPOINT DEFINITIONS

### 9.1. Endpoint Definitions

#### 9.1.1. VTE Endpoints

A suspected new or progressive symptomatic VTE, in the same anatomical region, should be documented with the same imaging method used at Screening/Baseline. Suspected new or progressive VTE in a different anatomical region should be documented utilizing institutional standards. These images should be collected and be included in the primary source records. Thrombus resolution of the qualifying event will be measured by repeat imaging at the EOS visit (using the same modality as that which was used to diagnosis the thrombosis prior to enrollment). If an image has been captured prior to the EOS and it demonstrates complete resolution of the qualifying VTE, then a repeat image does not need to be done again at day 90. For purposes of the study, the complete resolution image will be the “EOS” image for the index event.

In the assessment of a new or progressive symptomatic thrombus, the following general definitions will be utilized;

**Symptomatic New VTE:** Symptomatic VTE confirmed by at least one radiographic test. Asymptomatic VTE within a venous segment noted to be patent on a prior imaging study. Symptomatic will be defined as: New or progressive signs and symptoms as judged by the investigator including but not limited to:

- Objective swelling;
- Pain or tenderness;
- Pitting edema;
- Erythema or cyanosis.

**All New VTE:** All VTE confirmed by at least one radiographic test.

**Stable VTE:** Follow-up study demonstrating stable clot burden utilizing the same imaging modality as the Screening Visit.

**Regression of VTE:** Follow-up study demonstrating regressed clot burden utilizing the same imaging modality as the Screening Visit.

**Progression of VTE:** Progression of clot burden on a follow-up study in terms of severity of occlusion, or involvement of new venous segments at any time after the initial diagnosis.

In the assessment of a new or recurrent PE, the following general definitions will be utilized;

**New PE:** Symptomatic PE confirmed by presence of an intraluminal filling defect of the pulmonary artery on CT angiography and/or a mismatched defect on a nuclear V/Q scan. All new PE's will be considered to be a symptomatic event.

**Stable PE:** Follow-up study demonstrating stable clot burden utilizing the same imaging modality as the Screening Visit.

**Regression of PE:** Follow-up study demonstrating regressed clot burden utilizing the same imaging modality as at the Screening Visit.

**Progression of PE:** Progression of clot burden on a follow-up study in terms of involvement of new pulmonary arterial segments within 14 days after the initial diagnosis or PE.

Determination of the above definitions will be made utilizing set criteria based on clot location and imaging modality utilized.

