### **5.3. Definition of End of Study and Early Discontinuation**

End of study (EOS) is defined as Day 90 ( $\pm$  14 days) after study Baseline. Early Discontinuation from Study Drug: Early discontinuation from study drug treatment will be defined as less than 90 days of study treatment for cancer patients. For non-cancer patients, between 6 weeks and 3 months, rather than shorter or longer durations (Grade 2C), following completion of the PD Phase (2012 ACCP Guidelines) due to: 1) new or recurrent VTE; 2) bleeding necessitating permanent discontinuation of anticoagulant therapy; 3) unexpected permanent discontinuation of anticoagulant therapy; 4) AEs necessitating discontinuation of study drug; 5) withdrawal of consent to participate in the

trial, or 6) inability to achieve therapeutic range during Dose Adjustment Phase. Non-cancer patients will be required to remain in the study, however, for the full 3 months, regardless of dalteparin treatment duration.

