#### **6.2. Inclusion Criteria**

Subjects who meet all of the inclusion criteria and none of the exclusion criteria will be eligible for entry into the study.

Subjects meet inclusion if all of the following are true:

1. Have been objectively diagnosed with a venous thrombotic event documented using one of the following acceptable imaging modalities within 4 days of the Screening Visit:
  - Compression ultrasound with Doppler [CUD];
  - Computed tomography with/without venography [CT/CTV];
  - Magnetic resonance imaging with/without venography [MRI/MRV];
  - Conventional venography [CV];
  - Ventilation-perfusion scan [V/Q] (for pulmonary artery);
  - Spiral CT angiography [SCTA];
  - Conventional pulmonary angiogram [CPA].
2. Are judged clinically to require anticoagulation therapy.
3. Are in the age range of  $\geq 36$  weeks gestation and  $< 19$  years at the Screening Visit.
4. Have given signed informed consent (and assent, as appropriate) to participate prior to the Screening Visit.
5. For cancer patients only, a diagnosis of active malignancy (currently under treatment), other than basal cell or squamous cell carcinoma of the skin.
6. Male subjects able to father children and female subjects of childbearing potential and at risk for pregnancy must agree to use a highly effective method of contraception throughout the study and for at least 28 days after the last dose of assigned treatment.
7. Willing and able to comply with scheduled visits, treatment plan, laboratory tests, and other study procedures.
8. Female subjects of non-childbearing potential must meet at least 1 of the following criteria:
  - a. Achieved post-menopausal status, defined as follows: cessation of regular menses for at least 12 consecutive months with no alternative pathological or psychological cause; (status may be confirmed with/and have) (select one as appropriate) a serum follicle-stimulating hormone (FSH) level confirming the post-menopausal state;
  - b. Have undergone a documented hysterectomy and/or bilateral oophorectomy;
  - c. Have medically confirmed ovarian failure.

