### **9.3. Treatment Period**

This Baseline assessment can be conducted within 4 days of the Screening visit. If the Screening visit is conducted within 48 hours of the Baseline visit, the Medical History, Physical Exam (including weight and height), Pregnancy Test, Imaging and Clinical Labs (Chemistry, Antithrombin and Hematology) do not need to be repeated at the Baseline visit.

Baseline- Day 1 –The first study drug dose is administered. The subject could potentially have their first dose adjustment conducted on Day 1 if the Investigator deems it appropriate.

The following procedures will be conducted:

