##### **6.1.2.1. Efficacy Analysis**

- Proportion of subjects with objectively documented new or progressive symptomatic VTE during dalteparin treatment.

The count and proportion will be summarized overall and by each age group, along with the two-sided exact 95% CI.

- Relationship between objective documented new or progressive symptomatic VTE assessed by investigators and the anti-Xa level during dalteparin treatment.

Logistic regression for new/progressive VTE assessed by investigators on anti-Xa level at end of dose adjustment and other prognostic factors (eg, age, baseline tumor status), will be performed. For each of the covariates, the odds ratio, and the corresponding 95% CI, will be displayed.

Subjects who experience at least one new or progressive VTE while on study will be counted as Yes.

- Time to event (first episode of recurrent VTE) during dalteparin treatment.

The time to event (first recurrent VTE) will be described by using the Kaplan-Meier method. In addition, the Cox Proportional Hazard Regression model will be employed to assess the hazard ratio of the event with prognostic factors.

See [Appendix 1](#) for a general description of censoring of time-to-event variables.

- Proportions of subjects with progression, regression, resolution and no change in the qualifying VTE (in comparison with the assessment at study entry) during dalteparin treatment.

The count and proportion will be summarized overall and by each age group, along with the two-sided exact 95% CI.

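### Progression of a qualifying PE counts only within 14 days of diagnosis, so it cannot be met on the one scheduled follow-up image at Days 75-104

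*Protocol*

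**What the plan says.** Protocol Section 9.1.1 gives PE its own set of classes (new, stable, regression, progression) beside the general VTE set. Progression of PE is an increase in clot burden shown by "involvement of new pulmonary arterial segments within 14 days after the initial diagnosis or PE". The general VTE definition covers severity of occlusion "or involvement of new venous segments at any time after the initial diagnosis". Stable PE and Regression of PE carry no time limit.

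On timing of assessment, the same section says "Thrombus resolution of the qualifying event will be measured by repeat imaging at the EOS visit". An earlier image replaces it only if that image shows complete resolution. In the Protocol Flowchart (Table 1), the imaging row after Screening and Baseline is marked only at Visit 7/ET (Days 75-104) and at an Unscheduled Event. Visits 3 to 6 have no imaging. The flowchart notes make unscheduled imaging mandatory only when a recurrent or new VTE is suspected; otherwise it is at the investigator's discretion.

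PE can be the qualifying event: Section 6.2 accepts ventilation-perfusion scan, spiral CT angiography and pulmonary angiogram.

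SAP Section 6.1.2.1 reports "Proportions of subjects with progression, regression, resolution and no change in the qualifying VTE (in comparison with the assessment at study entry"), overall and by age group with exact 95% confidence intervals. It does not define progression.

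**The concern.** The endpoint sorts each qualifying clot into four outcomes, mainly from one late image. For PE, the unfavourable outcome expires long before that image is taken, while the neutral and favourable outcomes do not. A child whose PE has spread to new arterial segments by Visit 7 is not stable, not regressed and, by definition, not progressed. The nearest remaining class is New PE, and Section 9.1.1 says all new PEs are treated as symptomatic.

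Two things are at stake. The progression proportion can be too low for children entering with PE. Children entering with DVT and with PE are also scored by different rules in the same table. The central imaging reader and adjudication committee were removed (Protocol Document History, Amendment 7; SAP Section 1), so investigators at about 40 sites must apply this text themselves.

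**Working it through.** **Inputs**

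- Limit for PE progression: 14 days after diagnosis (Section 9.1.1).
- Diagnosis to Screening, a: 0 to 4 days, from "acceptable imaging modalities within 4 days of the Screening Visit" (Section 6.2).
- Screening to Baseline, b: 0 to 4 days, from "This Baseline assessment can be conducted within 4 days of the Screening visit" (Section 9.3). The flowchart puts Screening at Day -3 to Day -1, which is b = 1 to 3 with no Day 0.
- Baseline and first dose: Day 1.
- Scheduled follow-up image: Visit 7, Days 75-104 (Table 1).

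**Reproducing the visit window.** Three consecutive 30-day windows after Day 14 give Days 15-44, 45-74 and 75-104, which match Table 1. Section 5.3 says "End of study (EOS) is defined as Day 90" with a margin of 14 days either way, so 90 - 14 = 76 to 90 + 14 = 104. The one-day difference at the lower end does not affect the result.

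**When the 14-day window closes.** Let D = a + b be the days from diagnosis to Day 1. The window closes on study day 1 - D + 14 = 15 - D.

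| Source for b | D | Window closes |
|---|---|---|
| Section 9.3 | 0 to 8 | Day 15 to Day 7 |
| Flowchart | 1 to 7 | Day 14 to Day 8 |

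**Time from diagnosis to the Visit 7 image.** For an image on study day d this is (d - 1) + D.

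- Section 9.3: from 74 + 0 = 74 days to 103 + 8 = 111 days.
- Flowchart: from 74 + 1 = 75 days to 103 + 7 = 110 days.

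**Gap between window and image.** 75 - (15 - D) = 60 + D, so the smallest gap is 60 days (D = 0). No permitted schedule puts the planned image inside the window.

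**Classes open on the planned image for a qualifying PE**

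| Finding at Visit 7 | Class in Section 9.1.1 |
|---|---|
| Clot burden unchanged | Stable PE |
| Clot burden reduced | Regression of PE |
| New arterial segments, 74 to 111 days after diagnosis | Not Progression of PE; possibly New PE, otherwise none |

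**Scale, as illustration only.** Assuming a denominator of 50, the target number with viable PD data, one misclassified child moves the overall proportion by 1/50 = 2 percentage points. In an age group of 10, a stratum size considered in Section 12.1, one child moves it by 1/10 = 10 points. The number of such children cannot be derived from the documents.

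**The case against.** The strongest reply is that the 14-day limit was not written for this endpoint. The PE definitions are introduced as rules for assessing new or recurrent PE. The sentence in Section 9.1.1 that ties the qualifying event to the end-of-study image speaks of resolution. The SAP compares with study entry and mentions no 14 days. Section 9.1.1 also refers to further criteria by clot location and modality. On that reading, an analyst could call worsening at Visit 7 progression. This shows that the text is open to more than one reading, but it does not repair it. The SAP supplies no definition of progression that replaces the one in the protocol, and Stable PE and Regression of PE are themselves defined by comparison using the Screening modality.

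A second reply is that 14 days may be meant to separate progression from recurrence, which has its own endpoints. That is plausible, but no document says so, and none gives a class for later extension of the same PE.

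Three stronger readings might be inferred, and the documents do not support them:

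- *PE progression can never be recorded.* Suspicion of a new or recurrent VTE requires imaging, and early termination calls for it, so an image within 14 days is possible. One foreseeable source of very early termination is failure to reach the anti-Xa range within 7 days. Those children are outside the PD population used for efficacy.
- *A silent extension at Visit 7 necessarily enters the symptomatic endpoint.* The New PE definition opens by requiring symptomatic PE and only later treats every new PE as symptomatic, so the result is uncertain. The mixing is not peculiar to PE either: the definition of symptomatic new VTE also mentions asymptomatic VTE.
- *The separate PE radiographic criteria, which state no time limit, show that any time was intended.* That list pools new and progressive PE, has no timing rule and does not say that it replaces the 14-day limit.

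It also stands that the endpoint is secondary and exploratory, that the SAP plans no hypothesis tests and that no DVT-versus-PE comparison is planned.

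**Conclusion.** The point holds for the scheduled image. With diagnosis at most 8 days before first dose, the PE progression window closes by Day 15 at the latest and the planned image comes 60 or more days later. For children entering with PE, that image can show stable or regressed clot but not progression, whatever the true rate. The direction is known: the progression proportion can only be too low from this source, with late extensions left unclassified or moved to New PE.

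The size is unknown, because it depends on how many children enter with PE and how many extend late. The primary PD endpoints are unaffected. This is a definitional fault in a secondary, descriptive endpoint that should be corrected before analysis; it is not a threat to the trial's main conclusions.

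**What to change.** For the progression/regression/resolution/no-change endpoint only, add to Protocol Section 9.1.1 and SAP Section 6.1.2.1 that new pulmonary arterial segments on the end-of-study or early-termination image, compared with the study-entry image, count as progression of the qualifying PE regardless of time since diagnosis. State also that such a finding counts in the symptomatic new or progressive VTE endpoint, or in recurrent VTE, only if symptoms were present.

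If the 14 days is meant to separate progression from recurrence, say so and keep it as a labelled sub-class for those endpoints. In either case, reconcile the general VTE definitions, the PE definitions, the PE-specific radiographic criteria and the SAP text.

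Keep the change to endpoint scoring. Removing the limit throughout could alter what counts as a first recurrence and would touch the text in Sections 7 and 8.2 on when treatment ends, which should be left unchanged.

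The cost is a short clarification in each document, with no new visit or image. The progression proportion may turn out less favourable.
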